8.1.2 Serious Adverse Events

An SAE is defined as any untoward medical occurrence that at any dose:

1. **Results in death** – The event must be the cause of death for the SAE to meet this serious criterion.
2. **Is life-threatening** – The term “life-threatening” refers to an event in which the subject was at risk of death at the time of the event; it does not refer to an event that hypothetically might have caused death if it had been more severe.
3. **Requires in-patient hospitalization or prolongation of existing hospitalization** – The Sponsor considers “hospitalization or prolongation of existing hospitalization” for at least 24 hours as the defining criterion for an SAE. Hospital admissions for planned surgery or for normal disease management procedures (eg, chemotherapy) are not considered as defining criteria for SAEs.

4. **Results in persistent or significant disability or incapacity.**
5. **Is a congenital anomaly or birth defect.**
6. **Is medically significant** – A medically significant event is defined as an event that does not meet any of the other 5 SAE criteria, but which is judged by a physician to potentially jeopardize the subject or require medical or surgical intervention to prevent one of the above outcomes listed as an SAE criterion. Anaphylaxis that is successfully treated by administration of epinephrine prior to other sequelae is an example of a potentially medically important event.

For the purpose of data collection in this study, a prolonged seizure or series of seizures from which the subject does not regain consciousness between ictal events, that is at least 30 minutes in duration, is termed SE. A single episode of SE in a 24-hour period, regardless of whether rescue medication was administered, should be entered in the AE log as well as in the seizure diary. If two or more episodes occur within 24 hours, each lasting 30 minutes or more, an SAE of SE should be recorded. Hospitalization to manage SE, regardless of the number of episodes, should be reported as an SAE.

Adverse events that do not fall into the above categories are defined as nonserious AEs.

8.1.3 Adverse Events of Special Interest

As per ICH guidance ([E2F Development Safety Update Report 2011](#)), the Sponsor has identified the following AESI for the ZX008 program ([Table 14](#)).

Table 14. Adverse Events of Special Interest

Metabolic/Endocrine
1. Elevated prolactin level $\geq 2x$ above the upper limit of normal (ULN)
2. Hypoglycemia – serum blood glucose more than 20% below the glucose level on Day -1 value or more than 10% below LLN (reference range 60 – 140 mg/dL)
Neuropsychiatric
13. Suicidal thoughts, ideation or gestures
LLN = lower limit of normal; ULN = upper limit of normal

8.1.4 Adverse Events Requiring Hospitalization

If a subject is treated in a medical facility (hospital, emergency room, free-standing clinic) related to the occurrence of any AE, the following data will be collected to model health care utilization in patients with Dravet syndrome: AE/reason for hospitalization/clinic visit; duration of the visit in hours/days; admission to intensive care unit; and name/number of procedures performed, including but not limited to, electroencephalogram, ECG, ECHO, positive emission tomography (PET) scan, MRI, x-ray, computed tomography (CT) scan, surgery, and lumbar puncture/spinal tap.

8.2 SEVERITY OF ADVERSE EVENTS

The severity of AEs (whether nonserious or serious AEs) is to be assessed by the investigator as follows ([Table 15](#)).

Table 15. Severity Definition of Adverse Events

Severity	Definition
Mild	A type of AE that is usually transient and may require only minimal treatment or therapeutic intervention. The event does not generally interfere with usual activities of daily living.
Moderate	A type of AE that is usually alleviated with additional specific therapeutic intervention. The event interferes with usual activities of daily living, causing discomfort but poses no significant or permanent risk of harm to the research participant.
Severe	A type of AE that interrupts usual activities of daily living, or significantly affects clinical status, or may require intensive therapeutic intervention.

Clinical Data Interchange Standards Consortium Study Data Tabulation Model Severity Intensity Scale for Adverse Event Terminology

8.3 CAUSALITY OF ADVERSE EVENTS

The causal relationship of an AE to IMP must always be assessed by the investigator. All AEs will be classified as either **related** or **not related** to IMP. If a causality assessment is not provided for an AE (including an SAE), then that AE will be considered as related to IMP.

The degree of certainty with which an AE is attributed to IMP or an alternative cause (eg, natural history of the underlying disease, concomitant medications) will be determined by how well the event can be understood in terms of:

- Known pharmacology of ZX008
- Clinically and/or pathophysiologically plausible context
- Reaction of a similar nature previously observed with similar products, or reported in the literature for similar products as being product related (eg, headache, facial flushing, pallor)
- Plausibility supported by the temporal relationship (eg, the event being related by time to administration or termination of treatment with IMP drug withdrawal or reproduced on rechallenge)

The following classifications should be used in categorization of relatedness:

1. Not Related: Concomitant illness, accident or event with no reasonable association with study drug.

2. Related: The event follows a reasonable temporal sequence from administration of study drug and is definitive pharmacologically; cannot be attributed to concurrent disease or other factors or medications. A clinically reasonable response should be observed if the study drug is withdrawn or dose reduced.

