8.7 REPORTING OF SERIOUS ADVERSE EVENTS BY INVESTIGATOR TO IEC/IRB

The timeframe within an IEC/IRB must be notified of a death or an unexpected SAE considered at least possibly related to the IMP is stipulated by each individual IEC/IRB. The investigator is responsible for complying with the requirements for IEC/IRB notification. The investigator will notify the relevant IEC/IRB within the applicable timeframe by forwarding the safety report (eg, MedWatch/CIOMS form) completed by the Sponsor for the notifiable event.

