6.4.1 Adverse Events

An AE is defined as any unfavorable and unintended sign (including an abnormal, clinically significant laboratory finding), symptom, or disease temporally associated with the use of a medicinal (investigational) product, whether or not considered related to the medicinal (investigational) product. The period of observation for adverse events extends from the time the subject gives informed consent until the end of the titration/transition period (Visit 13). For patients who continue into the open-label extension study, AEs of special interest will continue to be monitored for up to 6 months after the last dose of study medication.

A TEAE is defined as any AE that based on start date information occurs after the first intake of study treatment. All other AEs occurring after enrollment and prior to the first administration of study treatment are defined as non-treatment emergent AEs (non-TEAEs).

Any missing relationship will be considered as “related.”

The severity of AEs (whether non-serious or serious AEs) will be assessed by the investigator as follows:

Severity Definition of Adverse Events:

Mild - A type of AE that is usually transient and may require only minimal treatment or therapeutic intervention. The event does not generally interfere with usual activities of daily living.

Moderate - A type of AE that is usually alleviated with additional specific therapeutic intervention. The event interferes with usual activities of daily living, causing discomfort but poses no significant or permanent risk of harm to the research participant.

Severe - A type of AE that interrupts usual activities of daily living, or significantly affects clinical status, or may require intensive therapeutic intervention.

Any missing severity will be imputed as “severe.”

The original terms used by the investigators in the eCRFs to identify AEs will be coded using the most recent version of the MedDRA implemented by the sponsor at the end of the study.

6.4.1.1 Overview of Events:

The number and percent of patients with at least one of the following events will be summarized in an overall summary table:

- TEAE.
- Serious TEAE
- Related TEAE
- Related serious TEAE.
- TEAE leading to treatment discontinuation
- Death

The percentage denominator for the calculation of percentage will be the number of subjects in the SAF.

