6.4.1.2 Treatment Emergent Adverse Events

The following summaries will display the number and percentage of subjects with adverse events by system organ class (SOC) and preferred term (sorted alphabetically) for each treatment group and overall:

- All TEAEs

- Serious TEAEs
- TEAEs by Maximum Severity
- Study Drug Related TEAEs
- All AEs that lead to premature discontinuation from the study

An additional summary will tally the number and percent of subjects in each treatment group who experience an AE that occurs in at least 5% of subjects. The summary will be presented by preferred term in decreasing order of incidence.

The summaries will be provided for the double-blind treatment period. No inferential statistical methods (i.e., methods that yield p-values) will be used to compare treatment groups on the frequency or severity of AEs.

Additionally, the following listings will be produced for all enrolled subjects:

- All AEs, events considered to be TEAE will be identified in the listing
- Serious AEs
- AEs that lead to premature discontinuation from the study
- Deaths

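### The two causality definitions in Protocol 8.3 are not exhaustive, so related-TEAE counts will depend on the investigator and are probably too low

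*Protocol*

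**What the plan says.** Protocol 8.3 allows two codes and defines each.

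- **Not Related:** "Concomitant illness, accident or event with no reasonable association with study drug".
- **Related:** the event follows dosing in a plausible time sequence "and is definitive pharmacologically; cannot be attributed to concurrent disease or other factors or medications". A further sentence adds an expectation about dechallenge: "A clinically reasonable response should be observed if the study drug is withdrawn or dose reduced".

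The same section lists matters to weigh (known pharmacology, clinical plausibility, similar reactions with similar products, timing). It says these determine "The degree of certainty with which an AE is attributed to IMP or an alternative cause", but it does not say what degree of certainty leads to which code.

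There is one default: "If a causality assessment is not provided for an AE (including an SAE), then that AE will be considered as related to IMP". SAP 6.4.1 repeats it for the analysis: "Any missing relationship will be considered as" related.

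Protocol 8.7 ties the IEC/IRB notification timeframe to a death or to "an unexpected SAE considered at least possibly related to the IMP".

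The code is used in two lines of the SAP 6.4.1.1 overview (related TEAEs and related serious TEAEs) and in the SAP 6.4.1.2 summary of "Study Drug Related TEAEs", which is Table 14.3.1.5b.

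**The concern.** A two-class scale works only if each class is the complement of the other. Here one class is reserved for events with no reasonable link to the drug, and the other for events whose link is definitive and has no competing explanation. Everything between has no home.

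In this trial the middle ground is large. Inclusion criterion 7 requires stiripentol, clobazam and valproate, or stiripentol with one of the other two where the third is contraindicated. Protocol 3.5 itself says that stiripentol can raise the levels and side effects of co-administered antiepileptics, and that CYP2D6 inhibition is likely to raise ZX008 levels. An event arising from that interaction has both ZX008 and a co-medication as plausible causes. Protocol 8.1.1 also counts worsening of seizures as an adverse event, and the underlying disease is always a candidate explanation for that.

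At stake is whether the related-TEAE and related-serious-TEAE counts mean the same thing from one site to the next, and whether they can be read as a measure of suspected drug effect.

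**Working it through.** The plan gives no figure on this point, so there is nothing to reproduce. The check is a clause-by-clause comparison, followed by a bound under stated assumptions.

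**Step 1. Apply both definitions to four kinds of event.**

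| Event | Meets Not Related? | Meets Related? |
|---|---|---|
| No reasonable link to ZX008 | Yes | No |
| Definitive link, no other attribution | No | Yes |
| Reasonable link, also attributable to epilepsy or a background antiepileptic | No (a reasonable association exists) | No (another attribution exists) |
| Reasonable but not definitive link, no other cause identified | No | No (not definitive) |

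The last two rows are the gap. A fatal or single transient event also cannot show the dechallenge response that the Related definition expects.

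**Step 2. Look for a rule that closes the gap.**

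- The default to Related covers only a missing assessment. Section 8.3 also says causality must always be assessed, so an assessed but ambiguous event never reaches the default.
- The list of matters to weigh is not mapped to either code.
- No sentence sends gap events to Not Related either.

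**Step 3. Compare the thresholds.** Section 8.3 offers a definitive effect or no reasonable association. Section 8.7 uses at least possibly related. The coded value therefore cannot show whether the 8.7 condition was met.

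**Step 4. Bound the undercount.** Let g be the share of truly drug-caused events that fall in the gap, and q the share of gap events coded Not Related. If drug-caused events outside the gap are coded correctly, then

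undercount of related events = g × q.

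Neither g nor q is in the documents. Both are assumptions:

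- q = 0, any g: 0%
- g = 0.9, q = 0.5: 0.9 × 0.5 = 45%
- g = 0.9, q = 0.9: 0.9 × 0.9 = 81%
- above 90%: impossible unless g and q both exceed 0.9

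The possible range is 0% to 100%.

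**Step 5. Trace what depends on the code.**

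- Affected: the two overview lines in SAP 6.4.1.1, Table 14.3.1.5b, and the wording of the 8.7 trigger.
- Not affected: all TEAEs, serious TEAEs, TEAEs by maximum severity and discontinuations due to AEs, all tabulated by arm without regard to relatedness (SAP 6.4.1.2). SAE reporting to the sponsor within 24 hours (8.6) and of all SAEs to the IRB/IEC (8.6.1) carries no causality condition.

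**The case against.** A reader might infer that related events will be almost entirely undercounted, that the direction of error is certain, and that ethics-committee notification is biased towards no drug effect. The case against this reading is strong, and most of it stands.

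- An event that fits neither definition is not thereby Not Related. The literal wording of that class excludes a plausible event just as the Related wording does. Near-total undercounting is one end of the range in Step 4, not a result.
- The only explicit default runs towards Related, in both the protocol and the SAP, and 8.3 tells investigators to weigh plausibility against alternatives. This counts against certainty of direction. It does not close the gap, for the reasons in Step 2.
- Background antiepileptics must have been stable for at least 4 weeks before screening, and a 6-week baseline follows. A new event after the IMP starts is not automatically attributable to an unchanged drug. This stands against any claim that almost no event could qualify as Related. It does not remove the events for which a second attribution is reasonable.
- On notification, 8.6.1 asks investigators to report all SAEs to the IRB/IEC, and 8.7 attaches no relatedness condition to deaths. Section 8.4 also requires sponsor reporting of a late SAE that could be associated with the IMP, whatever the investigator's causality opinion. What is left is inconsistent wording between 8.6.1 and 8.7, not a demonstrated failure to notify.
- The main safety comparison is randomized, blinded and descriptive, and does not use the code. Echocardiographic findings go through central reading and committee review rather than investigator causality. This limits the importance of the point but leaves the related-event tables as they are.

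**Conclusion.** The defect in the text is clear: 8.3 forces a binary choice with two definitions that are not complementary, and 8.7 uses a threshold the scale cannot record. Related-TEAE and related-serious-TEAE counts will be inconsistent between investigators.

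That they are probably too low is a judgement. It rests on the Related class carrying several demanding conditions at once while Not Related carries one, so an investigator in doubt may more often choose Not Related. The size is not determined by the documents, and they do not support a reading of certain or near-total undercounting. No conclusion drawn from the all-TEAE or serious-TEAE tables by arm is touched.

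The point is worth acting on because the rule cannot classify a kind of event that mandatory polytherapy should make common, and the repair is small.

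**What to change.** In Protocol 8.3:

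- Define Related as a reasonable possibility that the IMP caused or contributed to the event, even if another cause is also possible.
- Define Not Related as no reasonable possibility of this.
- Delete the clause "and is definitive pharmacologically; cannot be attributed to concurrent disease or other factors or medications". If the dechallenge sentence is kept, word it as supporting evidence and not as a condition, or part of the gap will reopen.

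In Protocol 8.7, use the same threshold as 8.3, and reconcile the section with 8.6.1 so that one statement governs which SAEs go to the IEC/IRB.

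The cost is two sentences in 8.3, a matching edit in 8.7 and an update to the eCRF completion guide. The SAP tables need no change in structure. The downside is that more events will be listed as related, including some caused by epilepsy or background medication; the tabulation by arm against placebo lets a reader judge these.

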8.4 OBSERVATION PERIOD FOR ADVERSE EVENT REPORTING

The observation period for AE and SAE reporting in an individual subject will start at the time of giving written informed consent for participation in the current study and finish 15 days after the last dose of study drug or the last visit, whichever is later. For subjects who enroll in the open-label extension trial, ongoing AEs will be followed in that study.

If the investigator becomes aware of an SAE that has started after the observation period has finished, and the event could in some way be associated with IMP (irrespective of whether or not it is considered by the investigator to be causally related to IMP), then this must also be reported to the Sponsor (see [Section 8.6](#)).

8.5 ADVERSE EVENT REPORTING

8.5.1 Adverse Events

At each clinical evaluation, the investigator (or delegate) will determine whether any AEs have occurred. Adverse events will be recorded in the AE page of the eCRF. If known, the medical diagnosis of an AE should be recorded in preference to the listing of individual signs and symptoms. The investigator must follow up on the course of an AE until resolution or stabilization. If an AE is ongoing after the end of study visit, the AE will continue to be followed up until resolution or stabilization.

If, during the study period, a subject presents with a pre-existing condition that was not noted at the time of study entry, the condition should be retrospectively recorded in the Medical History section of the eCRF.

8.6 SERIOUS ADVERSE EVENTS REPORTING

This study will comply with all applicable regulatory requirements and adhere to the full requirements of ICH Topic E2A ([Clinical Safety Data Management: Definitions and Standards for Expedited Reporting 1994](#)).

In the event of an SAE the investigator or delegate must:

1. Enter all relevant information in the AE page of the eCRF.
2. Inform the Medical Monitor or the Sponsor of the SAE via email or telephone within

24 hours of becoming aware of the SAE.

3. Follow the initial notification with a completed SAE report form. The SAE form must be emailed or faxed to Inventive Health Care within 24 hours of becoming aware of the SAE.

All SAEs that occur during the course of the study, beginning the day Informed Consent is signed, whether or not causally related to IMP must be reported immediately via telephone or email (within 24 hours of the investigator becoming aware of the event) to the Sponsor or the Medical Monitor.

Contact details and guidance for reporting SAEs will be provided to study site before the study starts.

8.6.1 Requirements for Immediate Reporting of Serious Adverse Events

The minimum reporting requirements for immediate reporting of SAEs include:

1. Identifiable subject
2. Suspected drug product
3. Event description
4. Identifiable reporting source

In addition, the investigator must:

1. Report all SAEs to the relevant IRB/IEC within the timeframe specified by the IRB/IEC.
2. Submit follow-up reports to the Sponsor Global Clinical Safety and Pharmacovigilance and the Medical Monitor until the SAE has resolved, or, in the case of permanent impairment, until stabilized.
3. Ensure that the AE term(s) and causality assessment for all SAEs is entered in the eCRF.

If the minimum requirements for reporting are fulfilled, the investigator should not wait to receive additional information to fully document the event before notifying the Sponsor.

When submitting SAE reports to the Sponsor, subjects should be identified only by their subject number and study number. The investigator should not include the subject's name and address.

SAE Update reports can be submitted to the Sponsor any time that additional relevant information becomes available. In cases of death, the investigator should supply the Sponsor and the IEC/IRB (as applicable, see [Section 8.7](#)) with any additional requested information as it becomes available (eg, autopsy reports and detailed medical reports). Once an SAE is reported to the Sponsor's Safety Group, a Safety Specialist may contact the investigator with follow-up questions.

The procedure to be followed if an ongoing AE becomes an SAE after the end of the observation period for AEs is described in [Section 8.9](#).

8.7 REPORTING OF SERIOUS ADVERSE EVENTS BY INVESTIGATOR TO IEC/IRB

The timeframe within an IEC/IRB must be notified of a death or an unexpected SAE considered at least possibly related to the IMP is stipulated by each individual IEC/IRB. The investigator is responsible for complying with the requirements for IEC/IRB notification. The investigator will notify the relevant IEC/IRB within the applicable timeframe by forwarding the safety report (eg, MedWatch/CIOMS form) completed by the Sponsor for the notifiable event.

8.8 REPORTING OF EVENTS OTHER THAN SERIOUS ADVERSE EVENTS BY INVESTIGATOR TO SPONSOR

Even if none of the criteria for an SAE are fulfilled, any of the following events must be reported by the investigator to the Medical Monitor within 72 hours from the time the investigator is notified.

1. Hypersensitivity reactions
2. Pulmonary hypertension
3. Cardiac symptoms requiring intervention, or valvulopathy, if identified outside of study-related monitoring

8.9 FOLLOW-UP OF ADVERSE EVENTS

Every effort should be made to follow-up subjects who continue to experience an AE or an SAE on completion of the study or until the AE resolves. All follow-up information (and attempted follow-up contacts) should be documented in the subject's medical records. Details of the subject's progress should also be submitted to the Sponsor's Global Clinical Safety and Pharmacovigilance and the Medical Monitor.

Subjects who are discontinued from the study or complete the study and have been found to have any signs of valvulopathy or pulmonary hypertension on ECHO will be followed until the condition has resolved or stabilized where no further changes are likely, for a minimum of

6 months from the last dose of study medication, unless it is determined after unblinding that the subject did not receive ZX008. In the event of an SAE a blood sample for ZX008 and AED PK should be collected as soon as feasible (this is not required for SAEs that occur before dosing with study medication).

